We will use a custom set of silver/silver chloride electroencephalographic (EEG) electrodes as described in McKinley et al.²¹ These new electrodes were shown to be more stable over time, produce lower sensation levels, and produce fewer skin reactions when compared to standard sponge electrodes. Both the anode and cathode consist of a separate array of 5 EEG electrodes as pictured in Fig. 1. Each electrode has an inner diameter of 1.6 cm yielding a contact area of 2.01 cm² for each electrode. At 2 mA of supplied current, the average current density will be 0.199 mA/cm² as calculated by current (2 mA) divided by area (10.05 cm²).

For the active anodal stimulation condition, tDCS will be applied at 2mA for 30 min. Sham tDCS will be applied at the same intensity but for only 30 seconds.¹ The anode will be applied to scalp location F3 according to the 10-20 EEG electrode placement system while the cathode will be placed over the contralateral (i.e. right) bicep. Electrodes will be secured using medical bandages, and connectivity will be ensured using highly conductive gel.¹

IV. Data Analysis

Sample size:

The sample size is selected such that we have power to detect differences in the mean reciprocal reaction time (mean 1/RT) and ESS, which are our co-primary endpoints. Differences in co-primary endpoints will be assessed at Visit 4. We assume a loss to follow up rate of 15%.

We will enroll a total of 60 patients with 30 randomized to each group. Thus we anticipate at least 50 evaluable patients. We will control the type I error rate at 0.05 for assessing the primary endpoints conservatively using a Bonferroni correction. With this sample size, we have 80% power to detect a change of 0.90 standard deviations in mean 1/RT with an alpha level of 0.025 using a two-sided t-test. For the ESS, we assume a standard deviation of 3.2²² and have 80% power with this sample size to detect a change in ESS of 2.87 with an alpha level of 0.025 using a two sided t-test.

Statistical Methods:

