The primary analysis will examine the co-primary endpoints. To analyze differences in mean 1/RT at Visit 4, we will use a linear regression model that is adjusted for baseline average inverse response time. To analyze differences in ESS at Visit 4, we will use a linear regression model that is adjusted for baseline ESS. We will employ a sequential testing procedure to control familywise type I error at 0.05 where we first test differences mean 1/RT and then test ESS.²³ If an endpoint is not stopped for early efficacy, it will be tested at the remaining alpha level, 0.023. If there is a significant difference in mean 1/RT, then ESS will instead be tested at the total remaining alpha level, 0.046.

Figure 1. tDCS electrode array (anode only pictured). All five elements are standard silver-silver chloride EEG electrodes placed in a plastic cup which is then filled with a conductive gel.¹

Secondary analyses will include additional outcomes from the PVT and subjective questionnaires. To analyze differences in the number of lapses at Visit 4, we will use a Poisson regression model to compare the lapse rate of the treatment group to that of the control group that adjusts for the baseline lapse rate. Additional subjective sleep scores and questionnaires will be assessed using linear regression that adjusts for baseline sleep and questionnaire scores respectively. We will also explore differences in the magnitude of the change pre and post treatment at Visit 1 and pre and post treatment at Visit 4. Characteristics of participants will be summarized by randomized treatment group using appropriate descriptive statistics. We will also summarize any reported side effects of treatment. Additional exploratory analyses may be conducted at the discretion of the study team.

Interim Analysis

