An interim analysis will be conducted after 34 patients have completed the study. The study will be stopped early for efficacy if both endpoints achieve the stopping boundaries. The analysis will assess both co-primary endpoints using the error spending approach described by Lan and Demets with the O'Brien-Fleming boundary.^{24,25} For reaction time, the stopping boundary will be achieved if the two-sided p-value is less than 0.005 ($|Z|>2.813$). If early efficacy is achieved for reaction time, early efficacy for ESS will be evaluated and calculated using the total available type I error rate of 0.05. In that case, the stopping boundary will be achieved if the one-sided p-value is less than 0.013 ($|Z|>2.48$). If early efficacy is not achieved for reaction time, then the stopping boundary for ESS will be achieved if the two-sided p-value is less than 0.005 ($|Z|>2.813$).

V. Event Reporting

(a) Adverse Events

The ICH Guideline for Good Clinical Practice E6(R1) defines an adverse event (AE) as:

Any untoward medical occurrence in a patient or clinical investigation subject administered a pharmaceutical product and which does not necessarily have a causal relationship with this treatment. An AE can therefore be any unfavorable and unintended sign (including an abnormal laboratory finding), symptom, or disease temporally associated with the use of a medicinal product, whether or not considered related to the medicinal product.

As this is a study that does not include a pharmaceutical product intervention, this definition would include AEs that occur as a result of protocol procedures and protocol treatment.

A serious adverse event (SAE) is any AE that:

- Results in death
- Is immediately life-threatening

This term refers to an event in which the subject was at risk of death at the time of the event; it does not refer to an event that may have led to death.

- Requires inpatient hospitalization or prolongation of existing hospitalization

In general, hospitalization signifies that the subject has been detained (usually involving at least an overnight stay) at the hospital or emergency ward for observation and/or treatment that would not have been appropriate in an outpatient setting.

- Results in persistent or significant disability/incapacity
The term disability means a substantial disruption of a person's ability to conduct normal life functions.

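### The fixed final test levels (0.023 and 0.046) assume an unstated information fraction of 34/50, so above 50 evaluable patients strict 0.05 control for ESS is not guaranteed

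*Combined protocol and SAP*

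**What the plan says.** All the relevant text is in section IV, Data Analysis.

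- **Sample size.** "We will enroll a total of 60 patients with 30 randomized to each group". Loss to follow-up is put at 15%, and "Thus we anticipate at least 50 evaluable patients". On error control: "We will control the type I error rate at 0.05 for assessing the primary endpoints conservatively using a Bonferroni correction". Each endpoint is powered at a two-sided 0.025.
- **Interim Analysis.** "An interim analysis will be conducted after 34 patients have completed the study". The method is Lan-DeMets spending with the O'Brien-Fleming boundary. The 1/RT boundary is |Z|>2.813. If 1/RT crosses, the ESS boundary is |Z|>2.48; if not, it is |Z|>2.813. The study stops early only if both endpoints cross.
- **Statistical Methods.** "If an endpoint is not stopped for early efficacy, it will be tested at the remaining alpha level, 0.023". If mean 1/RT is significant, "ESS will instead be tested at the total remaining alpha level, 0.046". The stated aim is familywise type I error control at 0.05.

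Neither the information fraction nor the final sample size behind these levels is given. Nothing says that the final levels will be recalculated from the number of patients analysed.

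**The concern.** Error spending fixes how much alpha is used at each look. The final critical value then depends on the correlation between the two looks, which is the square root of the information fraction. If more patients are evaluable than assumed, the interim is a smaller share of the total, the two statistics are less correlated, and a fixed final level spends more than the alpha left.

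The plan treats 50 as a lower limit, so a final count above 50 is what it anticipates. At stake is the claim of strict control at 0.05. There is also a practical risk: if the final ESS p-value falls between about 0.044 and 0.046, the conclusion could depend on whether the printed level or the recomputed one is used, and the plan would not settle it.

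**Working it through.** **Inputs.** Interim at 34 completers and boundaries 2.813 and 2.48 (Interim Analysis); final levels 0.023 and 0.046 (Statistical Methods); 60 enrolled and 15% loss, so 60 × 0.85 = 51, with at least 50 evaluable (Sample size).

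**Step 1. Reproduce the plan's figures.** The O'Brien-Fleming-type spending function applied to each tail gives

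alpha spent at t = 4 × [1 − Φ(z(1−α/4)/√t)].

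With t = 34/50 = 0.68 and √t = 0.8246:

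- α = 0.025: 2.4977/0.8246 = 3.0289; spent 0.0049; interim boundary 2.813; final critical value 2.266; final level 0.02345.
- α = 0.05: 2.2414/0.8246 = 2.7181; spent 0.0131; interim boundary 2.480; final critical value 1.9956; final level 0.0460.

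Both boundaries and both final levels match the plan, with 0.02345 printed as 0.023. The levels therefore belong to 34/50.

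**Step 2. Hold the printed levels fixed and vary the final n.** For interim cut-off c1 and final cut-off c2,

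total error = P(|Z1|>c1) + P(|Z1|≤c1 and |Z2|>c2),

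where Z1 and Z2 are bivariate normal with correlation √(34/n). The level 0.046 gives c2 = 1.9954, and 0.023 gives c2 = 2.2734.

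| Final n | 34/n | A: ESS, 2.48 then 0.046 | B: ESS, 2.813 then 0.046 | C: either endpoint, 2.813 then 0.023 |
|---|---|---|---|---|
| 44 | 0.773 | 0.0485 | 0.0464 | 0.0240 |
| 48 | 0.708 | 0.0496 | 0.0467 | 0.0244 |
| 50 | 0.680 | 0.0500 | 0.0469 | 0.0246 |
| 51 | 0.667 | 0.0502 | 0.0469 | 0.0247 |
| 54 | 0.630 | 0.0508 | 0.0471 | 0.0249 |
| 55 | 0.618 | 0.0510 | 0.0472 | 0.02496 |
| 56 | 0.607 | 0.0511 | 0.0473 | 0.02503 |
| 60 | 0.567 | 0.0517 | 0.0475 | 0.0253 |

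Column A applies when 1/RT crosses at the interim. Column B applies when 1/RT misses at the interim and wins at the end. Column C applies to 1/RT itself, and to ESS when 1/RT never wins.

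**Step 3. Weight the paths for a given 1/RT effect.** Take ESS null and the two endpoints independent. At the design effect of 0.90 SD, 1/RT crosses at the interim with probability 0.425.

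- n=51: 1/RT wins only at the end with probability 0.404. ESS error = 0.425 × 0.0502 + 0.404 × 0.0469 + 0.171 × 0.0247 ≈ 0.0445.
- n=60: the corresponding probability is 0.4645. ESS error = 0.425 × 0.0517 + 0.4645 × 0.0475 + 0.1105 × 0.0253 ≈ 0.0469.

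At 1.5 SD, 1/RT crosses at the interim with probability 0.941, and the ESS error is 0.0500 at n=51 and 0.0515 at n=60. At 2.5 SD it is essentially column A.

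With both endpoints null and independent, familywise error is 1 − (1 − C)²: 0.0487 at n=51 and 0.0499 at n=60.

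**Step 4. Levels that restore the target**, given the planned interim boundaries:

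| Final n | Level keeping 0.025 | ESS level keeping 0.05 |
|---|---|---|
| 51 | 0.02336 | 0.04575 |
| 54 | 0.0231 | 0.0451 |
| 60 | 0.0227 | 0.0441 |

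**The case against.** The printed levels are arithmetically correct at the plan's own figure of 50. The worst-case excess at the 51 implied by 15% loss is 0.0002, about the size of rounding in three-decimal levels. The largest excess, 0.0017, needs no dropout at all and a near-certain interim crossing by 1/RT. All of this stands, and it is why the priority is low.

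A reader might infer two stronger things that the documents do not support.

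- *That the levels are valid only at exactly 50.* Both are conservative below 50, and 0.023 keeps its 0.025 through n=55.
- *That the ESS error exceeds 0.05 whenever more than 50 patients are evaluable.* The 2.48 boundary is available only if 1/RT crosses at the interim. Otherwise the ESS error is at most about 0.0475. At the plan's 0.90 SD effect it is about 0.045 to 0.047, and correlation between the endpoints lowers it further. With both endpoints null, familywise error stays just under 0.05 up to n=60.

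The objection does not remove one point. Strict familywise control must hold whatever the true 1/RT effect, including one large enough to cross at the interim almost surely. In that case the rule as printed exceeds 0.05 at every n from 51 to 60.

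**Conclusion.** The concern holds as a small gap in the specification, not as a miscalculation. The final levels are tied to an unstated 34/50, and no step adjusts them to the number analysed. Above 50 evaluable patients, strict 0.05 control for ESS is not guaranteed: the worst case is 0.0502 at n=51, 0.0508 at n=54 and 0.0517 at n=60. For the 0.023 level, the allowed 0.025 is first passed at n=56 and reaches 0.0253 at n=60.

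These figures rest on the following assumptions:

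- a normal approximation to the regression tests;
- information proportional to the number of patients;
- an interim at exactly 34;
- 2.48 read as a two-sided boundary (two-sided p = 0.0131), although the Interim Analysis text labels the 0.013 one-sided;
- an interim crossing counted as a rejection of that endpoint.

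The range 51 to 60 is inferred from 60 enrolled and 15% loss; the plan itself says only at least 50.

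**What to change.** In Statistical Methods, state that 0.023 and 0.046 are the planned levels at an information fraction of 34/50. Then replace their use as fixed thresholds with a sentence such as:

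> Final critical values will be recomputed from the O'Brien-Fleming-type spending function, using the alpha spent at the interim and the actual information fraction (34 divided by the final evaluable n).

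This agrees with the error-spending method that the plan already names and needs no extra patients. The cost is that the ESS level becomes slightly stricter above n=50, down to 0.0441 at n=60. The 0.023 level becomes marginally looser through n=55 (0.02336 at n=51) and slightly stricter from n=56 (0.0227 at n=60).

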- Idiopathic Hypersomnia or Narcolepsy without Cataplexy (Narcolepsy Type 2). Idiopathic hypersomnia and narcolepsy without cataplexy are usually objectively differentiated based on the number of sleep onset rapid eye movement periods (SOREMP) during a multiple sleep latency test (MSLT). However, this diagnostic feature has been shown to be not stable over time making it difficult for clinicians to distinguish these two conditions.^{16,17}
- Hypersomnia in OSA patients adequately treated with positive airway pressure (PAP) therapy or dental device
- Posttraumatic hypersomnia
- Unspecified hypersomnia

Patients with Narcolepsy with Cataplexy will be excluded from this study in view of the specific known loss of hypocretin in these patients.

Informed consent will be obtained from all participants. If the subject is agreeable, the consent form will be sent to them via mail or electronically so that they will have the opportunity to read the document ahead of time.

B. Subject Selection:

1. Inclusion/Exclusion Criteria

A. Key Inclusion Criteria

- Age 18 - 70 years
- Epworth Sleepiness scale score >10
- Stable medication dosage over previous 4 weeks
- Able to understand English and read and write at the 8th grade level and give a written informed consent document.
- Stable sleep/wake schedule (that is, no rotating shift work)
- Clinical diagnosis of any of the following:
 - a. Idiopathic Hypersomnia
 - b. Narcolepsy without Cataplexy
 - c. Hypersomnia in OSA patients adequately treated with PAP therapy or dental device

- d. Posttraumatic hypersomnia
- e. Hypersomnia, unspecified
- Multiple sleep latency test (MSLT) shows fewer than two sleep onset REM periods (except for patients with Narcolepsy without cataplexy, a diagnosis that requires at least two sleep onset REM periods) and a mean sleep latency of \leq 8 minutes. An MSLT is not required for inclusion of OSA patients provided their Epworth Sleepiness Scale (ESS) score is >10 . Adequately treated OSA patients will be defined as: i) an average PAP usage of \geq 4 hours per night and a residual apnea-hypopnea index (AHI) of <10 /hour based on PAP machine download during at least a 30-day period, or ii) regular use of dental device during sleep based on self-report and a prior sleep study showing an AHI <10 /hour while using the dental device.

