- 2) Stanford Sleepiness Scale (SSS)
- 3) Functional Outcomes of Sleep Questionnaire (FOSQ-10)
- 4) Visual Analogue Scale (VAS)
- 5) Center for Epidemiologic Studies Depression Scale (CES-D)
- 6) Side Effects

6. Actigraphy

This device is the size of a small wristwatch that measures activity and is a non-invasive method of monitoring human rest/activity cycle. The instructions for the device use as well as a sleep diary will be provided. The data is then downloaded into a computer.

7. Psychomotor Vigilance Test (PVT)/Cognitive Tasks

The PVT is a sustained-attention, reaction-timed task that measures the speed with which subjects respond to a visual stimulus. The PVT is a simple task where the subject presses a button as soon as the light appears. The light will turn on randomly every few seconds for 10 minutes. The purpose of the PVT is to measure sustained attention and give a numerical measure of sleepiness.²¹ In addition, subjects will also be asked to make judgements or decisions on stimuli such as words or images presented on a computer screen to track memory and thought process (cognitive performance).

8. Transcranial Direct Current Stimulation (tDCS)- active and sham stimulation

The neuroConn DC stimulator (neuroCare Group, Munchen, Germany) will be used to provide the tDCS stimulation. This battery-powered device will be controlled with a microprocessor to ensure constant current at up to 2000 μ A. For safety, multistage monitoring of the output current and electrode/tissue impedance will be included. The device automatically shuts off if the impedance becomes greater than 50 k Ω to prevent electric shocks or burns. This device will be investigational only (not FDA approved). As above, tDCS is a non-significant risk (NSR) investigational device that meets the abbreviated Investigational Device Exemptions (IDE) requirements at 21 CFR 812.2(b) addressing labeling, IRB approval, informed consent, monitoring, records, reports, and prohibition against promotion for an NSR device study.

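### The secondary PVT lapse count is analysed by Poisson regression with no provision for overdispersion, so its stated precision is too optimistic if residual variance exceeds the mean

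*Combined protocol and SAP*

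**What the plan says.** Section IV, Statistical Methods, makes lapses a secondary outcome: "Secondary analyses will include additional outcomes from the PVT and subjective questionnaires". The method follows. "To analyze differences in the number of lapses at Visit 4", the plan specifies this method: "Poisson regression model to compare the lapse rate of the treatment group to that of the control group that adjusts for the baseline lapse rate". That is the whole specification. No section mentions overdispersion, a dispersion check, a scale parameter, robust standard errors, a negative binomial model or a fallback. The only latitude is a general allowance for exploratory analyses at the study team's discretion.

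Three other places bear on the point:

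- **Length of the test** (III.D.7): "The light will turn on randomly every few seconds for 10 minutes".
- **Who is enrolled** (III.B.1, Key Inclusion Criteria): "Clinical diagnosis of any of the following", followed by five hypersomnia diagnoses.
- **How many are analysed** (IV, Sample size): "We will enroll a total of 60 patients with 30 randomized to each group", and "Thus we anticipate at least 50 evaluable patients".

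**The concern.** Model-based Poisson standard errors are correct only if no between-patient variation in lapse rate remains after adjustment. If some remains, residual variance is larger than the mean. The standard error is then too small, the interval too narrow and the p-value too low.

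Adjusting for baseline removes part of that variation. But the baseline is one count from one short test, so it measures each patient's underlying rate with error. The rate may also change between Visit 1 and Visit 4.

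What is at stake is over-reading of one secondary result. Vigilance is the trial's first objective, and lapses are the only additional PVT outcome given its own named model. A falsely narrow interval could therefore be taken as support for a vigilance effect.

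**Working it through.** **Inputs.** From the documents: the Poisson model adjusted for baseline, 30 randomised per arm, 15% loss and at least 50 evaluable. The plan states no figure for the lapse analysis, so there is none to reproduce. The number analysed is consistent: 60 × 0.85 = 51. A noncentral t calculation with 25 per arm at two-sided alpha 0.025 gives 80.4% power for 0.90 SD and 80.1% for 2.87/3.2 on the ESS, against the stated 80%. So 25 per arm is the right basis.

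Assumed, because the documents do not give them: the lapse mean, its variance, the between-visit correlation, and a two-sided 5% test.

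**Step 1: direct formula.** If residual variance is φ times the mean, the true standard error is √φ times the reported one. The actual type I error is 2 × (1 − Φ(1.96/√φ)). For φ = 2, 1.96/1.414 = 1.386, giving 0.166.

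| φ | True SE / reported SE | Type I error | Coverage of the 95% interval |
|---|---|---|---|
| 1 | 1.0 | 5% | 95% |
| 1.5 | 1.2 | 11% | 89% |
| 2 | 1.4 | 17% | 83% |
| 3 | 1.7 | 26% | 74% |
| 5 | 2.2 | 38% | 62% |

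**Step 2: does baseline adjustment bring φ to 1?** Take the case kindest to the plan, in which each patient's true rate is identical at both visits. With gamma-distributed rates of mean m and shape k, the unadjusted ratio is 1 + m/k. Given one baseline count, the Visit 4 count is negative binomial with ratio 1 + m/(m + k). For m = 5 and k = 2 these are 1 + 5/2 = 3.5 and 1 + 5/7 = 1.7. Adjustment halves the ratio but cannot bring it to 1.

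**Step 3: simulation under no effect.** 25 per arm, Poisson model with treatment and log(baseline + 1), 4,000 trials per scenario. The three low-heterogeneity rows come from a separate run; their unadjusted ratios are 1 + m/k.

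| Mean; shape; between-visit correlation | Ratio before adjustment | Ratio after | Poisson type I error |
|---|---|---|---|
| 3, 5 or 10; no heterogeneity | 1 | 1 | 4.5% to 5.0% |
| 1; 4; 0.9 | 1.25 | about 1.2 | 6.1% |
| 2; 10; 0.9 | 1.2 | about 1.2 | 7.0% |
| 3; 10; 0.9 | 1.3 | about 1.2 | 7.4% |
| 3; 4; 0.8 | 1.7 | 1.5 | 11.6% |
| 5; 2; 1.0 | 3.4 | 1.7 | 13.5% |
| 5; 2; 0.8 | 3.4 | 2.3 | 20.4% |
| 10; 1; 0.7 (deliberate extreme) | 10.8 | about 6.2 | 44.9% |

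In the 4,000-trial scenarios, scaling by the Pearson dispersion with a t reference on 47 degrees of freedom gave 4.5% to 5.5%, and 6.7% at the extreme.

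**Step 4: does this depend on the gamma assumption?** With lognormal rates (mean 5 or 10, log-SD 0.5 or 0.8, correlation 0.7 to 0.9; 1,500 trials each), residual φ was about 1.8 to 4.8. Poisson type I error was 15% to 42%, against 4.7% to 7.0% after Pearson scaling.

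**The case against.** The strongest reply is that the plan is silent on the variance rather than wrong about it. It names an outcome, a mean model and a covariate, and does not say that model-based standard errors will be used. That is literally true. But a Poisson model as named fixes variance at the mean, and nothing else in the document changes that. The exploratory allowance is no remedy, because it leaves the variance method to be chosen after the data are seen.

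Second, every magnitude above 5% rests on assumed inputs. This stands. Low-heterogeneity inputs are as compatible with the documents as the others, and they inflate the error by only one to three percentage points. The extreme row shows where the mechanism leads and says nothing about this trial in particular.

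Third, the entry criteria also narrow the sample: ESS above 10, stable medication and sleep schedule, no current stimulants, and no habitual sleep under 7 hours. The net effect on heterogeneity cannot be determined from the documents. The finite number of stimuli does not rescue the model either. An assumed cap of 90 moved the type I error for mean 5, shape 2, correlation 0.8 only from 20.9% to 19.8% in a repeat run.

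Fourth, lapses carry no alpha, power claim or decision rule. This also stands, and it limits the weight of the point.

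**Conclusion.** The concern holds in its conditional form. The plan makes no provision for overdispersion, and if variance exceeds the mean after baseline adjustment, the standard error, interval and p-value for lapses are too optimistic. Some residual overdispersion is likely, because a single short baseline test cannot remove all between-patient variation. How much there will be cannot be known from the documents.

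Over the assumed scenarios, leaving out the deliberate extreme, the nominal 5% test rejected between about 5% and 20% of the time under no effect. The rate ratio estimate itself is not in question, only its stated precision. Lapses lie outside the familywise procedure, which covers only mean 1/RT and ESS, so the co-primary tests, sample size and interim boundaries do not change. The point deserves correction but does not threaten the trial's main conclusions.

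**What to change.** Prespecify Poisson regression for Visit 4 lapses with an estimated Pearson dispersion and a t reference on the residual degrees of freedom. Keep the baseline adjustment, for example as log(baseline lapses + 1), and report the rate ratio with the resulting interval.

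Two alternatives are acceptable:

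- **Robust standard errors with a small-sample correction.** HC3 with a t reference gave type I error of 3.8% to 5.2%; HC1 with a normal reference gave 5.2% to 7.5%.
- **Negative binomial regression** (4.1% to 7.4%). This needs a named fallback: without overdispersion, the fit failed or the dispersion estimate reached its boundary in 56% to 58% of simulated trials.

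The cost is one sentence and one software option. The median scaled interval was 1.02 times the Poisson width with no overdispersion, 1.25 times with mean 3, shape 4, correlation 0.8, and 1.54 times with mean 5, shape 2, correlation 0.8. The 1.02 is a median: with no heterogeneity at mean 5, the scaled interval was narrower than the Poisson one in 44% of trials, because the estimated dispersion fell below 1. Type I error there was still 4.8%. The sentence should say whether estimates below 1 are used as they stand.

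### The interim ESS boundary that applies once reaction time has crossed is labelled a one-sided p of 0.013, but the |Z|>2.48 printed beside it is a two-sided p of 0.013

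*Combined protocol and SAP*

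**What the plan says.** All references are to Section IV, Data Analysis, of the combined protocol and SAP.

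- **Interim Analysis.** One look is planned after 34 completers, with Lan-DeMets spending and an O'Brien-Fleming boundary. The stopping rule is joint: "The study will be stopped early for efficacy if both endpoints achieve the stopping boundaries". The reaction-time boundary is a two-sided p below 0.005, |Z|>2.813.
- **ESS, if reaction time has crossed.** "If early efficacy is achieved for reaction time, early efficacy for ESS will be evaluated" with the full type I error of 0.05. In that case "the stopping boundary will be achieved if the one-sided p-value is less than 0.013", with |Z|>2.48 in parentheses.
- **ESS, if reaction time has not crossed.** "then the stopping boundary for ESS will be achieved if the two-sided p-value is less than 0.005", with |Z|>2.813.
- **Statistical Methods.** At the final analysis, after a significant reaction-time result, "ESS will instead be tested at the total remaining alpha level, 0.046". Otherwise an endpoint not already stopped is tested at 0.023.
- **Sample size.** "Thus we anticipate at least 50 evaluable patients". For ESS, with an SD of 3.2, the plan claims to "have 80% power with this sample size to detect a change in ESS of 2.87", using a two-sided t-test at 0.025.

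No section gives a reason for a one-sided ESS test in this single branch.

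**The concern.** One sentence states one threshold in two forms that are not the same threshold. Rounding of 0.013 does not bridge the gap.

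The threshold matters because stopping needs both endpoints to cross. Once reaction time has passed 2.813, the ESS result alone settles whether the trial stops. A favourable ESS statistic between about 2.23 and 2.48 stops the trial under the p-value wording and continues it under the Z wording. Two analysts programming from the same sentence could reach opposite recommendations, and the choice between them could be made with the interim data in view.

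The p-value wording also changes how alpha is spent. Read as benefit-only, it doubles the benefit tail at the interim from 0.0066 to 0.013. The total spent stays at 0.013, because nothing is then spent in the other tail.

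**Working it through.** **1. Convert the printed forms (no assumptions needed).**

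- |Z|=2.48: one-sided 1 − Φ(2.48) = 0.0066; two-sided 2 × 0.00657 = 0.0131.
- One-sided p = 0.013: Z = Φ⁻¹(0.987) = 2.226. For p from 0.0125 to 0.0135, Z runs from 2.241 to 2.212.
- Two-sided p = 0.013: |Z| = Φ⁻¹(0.9935) = 2.484. Over the same rounding range, |Z| runs from 2.498 to 2.470, which contains 2.48.

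The printed pair agrees only as a two-sided p-value.

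**2. Reproduce the plan's boundaries.** The information fraction is not stated. Assume t = 34/50 = 0.68, from 34 completers and 50 evaluable patients. With total two-sided alpha *a*, O'Brien-Fleming-type spending per side is 2[1 − Φ(z₁₋ₐ/₄ / √t)]. The final boundary comes from the bivariate normal with correlation √t.

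- *a* = 0.05: 2.2414/√0.68 = 2.718, so 0.00657 per side, Z = 2.480, two-sided p = 0.0131. Final nominal p = 0.0460.
- *a* = 0.025: 2.4977/√0.68 = 3.029, so 0.00245 per side, Z = 2.813, two-sided p = 0.0049. Final nominal p = 0.0234.

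These match the printed 2.48, 0.013 and 0.046, and the printed 2.813, 0.005 and 0.023. Other denominators do not: with *a* = 0.05, 34/51 gives Z = 2.509 and 34/60 gives Z = 2.758. One-sided spending at t = 0.68 does not give p = 0.013 either: one-sided alpha 0.05 gives 0.0175 (Z = 2.109), and 0.025 gives 0.0066 (Z = 2.480).

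**3. Type I error for ESS when this branch applies.** The final test is at two-sided 0.046 (|Z|>1.995). The printed cut-offs are held fixed while t varies.

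| Interim ESS rule | t = 34/50 | t = 34/51 | t = 34/60 |
|---|---|---|---|
| \|Z\|>2.48 | 0.0500 | 0.0502 | 0.0517 |
| Z>2.226, benefit only | 0.0515 | 0.0517 | 0.0530 |
| \|Z\|>2.226, either direction | 0.0570 | 0.0574 | 0.060 |

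At 34/50 the benefit tail over both looks is 0.0250 under the first rule and 0.0285 under the second.

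**4. Whole procedure.** Four million simulated trials, independent endpoints, t = 34/50:

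- Both endpoints null: familywise error about 0.049 under all three rules.
- Reaction-time effect 0.90 SD, ESS null: ESS error 0.044, 0.045 and 0.047, in the order of the table.

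**5. Effect on the stopping decision at the planned effects (17 per arm).**

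- Reaction time: mean Z = 0.90 × √(34/4) = 2.624; P(Z>2.813) = 0.425.
- ESS: mean Z = (2.87/3.2) × √(34/4) = 2.615; P(Z>2.48) = 0.554 and P(Z>2.226) = 0.651.
- Both cross, if independent: 0.425 × 0.554 = 0.235 against 0.425 × 0.651 = 0.277.

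**6. The disputed window in ESS points, without baseline adjustment.** SE = 3.2 × √(2/17) = 1.098. Then 2.226 × 1.098 = 2.44 and 2.48 × 1.098 = 2.72 points, against the planned 2.87.

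**The case against.** The strongest reply is that this is a wrong word beside a correct number, not two rules of equal standing. The absolute-value sign is two-sided notation, the other interim boundaries are labelled two-sided, ESS is powered with a two-sided test, and the named spending method returns 2.48. A statistician would probably use 2.48. That stands, and it is why the fix can be stated with confidence. It does not remove the contradiction, because confirming the intended value requires an information fraction that the plan never gives.

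The reply on size also largely stands. Error over the whole procedure stays below 0.05 in both simulated scenarios. The 0.0515 and 0.0570 describe ESS only when the reaction-time branch is taken, and 0.0570 needs a one-sided cut-off applied in both directions, which is not the natural reading. Part of the increase at 34/60 comes from using cut-offs that this fraction does not generate: even |Z|>2.48 gives 0.0517 there. Overall ESS power at the planned effects hardly moves (about 0.87 on either rule).

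Finally, the window of 2.44 to 2.72 points ignores the baseline adjustment that Statistical Methods specifies. An assumed baseline correlation of 0.5 would multiply the SE by √(1 − 0.25) = 0.866, moving the window to about 2.12 to 2.36 points. The window on the Z scale is unaffected.

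**Conclusion.** The concern holds: the sentence is wrong as written. That the two forms disagree follows from the normal distribution alone. That *one-sided* is the faulty word rests on the assumed fraction of 34/50, which is well supported because it reproduces both interim Z values and both final alpha levels.

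The consequence is an ambiguous decision rule, not a material loss of error control. It arises only at the interim, only after reaction time has crossed, and only for a favourable ESS statistic between about 2.23 and 2.48. Under the planned effects and independent endpoints, the choice of form shifts the chance of early stopping by about 4 percentage points (23.5% to 27.7%). It should be fixed because it is a pre-specified stopping threshold for a co-primary endpoint.

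**What to change.** In Interim Analysis, in the sentence giving the ESS boundary after reaction time has crossed, replace *one-sided* with *two-sided*, so that it reads as a two-sided p-value below 0.013 with |Z|>2.48. Keep 2.48, 0.013 and the final 0.046 unchanged.

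The cost is one word. The sample size, the Z boundaries and the final alpha levels all stay as they are.
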